4.8.2 Clinical Laboratory Evaluation

For Part A (SAD) and Part B (MAD) separately, the following clinical laboratory summaries will be provided for serum chemistry, hematology, coagulation and urinalysis (specific gravity and pH only).

- Continuous descriptive statistics of observed values and change from baseline by study visit;
- Summary tables by reference range indicator;
- Shift summary tables by reference range indicator

Unscheduled and early termination visits may not be summarized in the tables but will be presented in the listings.

The following by-subject laboratory listings (values and change from baseline if applicable) will be provided by study part and treatment group using the enrolled subjects:

- Serum Chemistry
- Hematology
- Coagulation
- Urinalysis
- Virus Serology (screening only)
- Serum and Urine Pregnancy test
- HLA DQ2.5 and HLA DQ8 testing (screening only)

- Transglutaminase and deaminated gluten peptides IgA/IgG (screening only)
- Lab abnormality experiencing \geq Grade 3 in Severity.

Toxicity, in reflection of safety laboratory results will be graded locally according to NCI-CTCAE v5.0 or higher and included in listings. If any laboratory value falls above or below the upper or lower level of quantification, the value of the upper or lower level of quantification will be used.

Protocol doesn't require Urine micro analysis under the microscope for urinalysis, leukocyte count, erythrocyte count, epithelial cell count and bacterial count. So, these parameters will be shown in the listings only.

There are tests with multiple standard units. "Standard-Unit" per test/subject will be taken into consideration in deriving the baseline. Post-baseline records will not have a 'Change' value if the unit doesn't match with baseline record unit for that subject and test.

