12.8. Clinical Laboratory Assessments

All statistical analyses of laboratory values will be performed using International System units. All statistical analyses will be by dose group.

Summary statistics for laboratory values including change from baseline will be tabulated for scheduled visits. Shifts in Grade from baseline to the maximum post-baseline (including unscheduled) grade will be summarized by number and percentage of patients within each category. Abnormality of laboratory data will be listed for patients with \geq Grade 3 in severity.

A listing of individual patient hematology, serum chemistry, and coagulation values outside the reference ranges will be provided. This listing will include data from scheduled and unscheduled timepoints.

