- The abnormal values will be flagged with 'LOW' for values below the lower limit of the local clinical reference range and 'HIGH' for values above the upper limit of the local clinical reference range and included in the listings.

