4.3.1 Non-PK Tables, Listings and Figures

- ‘Baseline’ is defined as the last available pre-treatment assessment, including any unscheduled assessment. Every effort will be made to ensure that accurate baseline information is collected. Subjects will not be excluded from any of the analysis populations due to missing baseline. However, if a subject is missing baseline information, they will have a missing change from baseline result.
- Continuous data will be summarized in terms of the number of observations (n), mean (arithmetic), standard deviation (SD), median, and range (minimum and maximum), unless otherwise stated.
- The minimum and maximum will be reported to the same number of decimal places as the raw data recorded in the database. The mean and median will be reported to one more decimal place than the raw data recorded in the database. The SD will be reported to two more decimal places than the raw data recorded in the database. In general, the maximum number of decimal places reported shall be four for any summary statistic.
- Categorical data will be summarized in terms of the number of subjects providing data at the relevant time point (n), frequency counts and percentages.

- Percentages will be rounded to the nearest one decimal place. Percentages will not be presented for zero counts. Percentages will generally be calculated using the number of subjects in a group (n) as the denominator, otherwise the method will be noted in a footnote.
- Unscheduled and early termination visits may not be summarized in the tables but will be presented in the listings.

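### The SAP drops the protocol's table of shifts to worst post-baseline CTCAE lab grade without declaring it, so the lab shift tables cannot show severity and may miss unscheduled worst values

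*SAP*

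**What the plan says.** Protocol 12.8 sets out the lab shift analysis: "Shifts in Grade from baseline to the maximum post-baseline (including unscheduled) grade will be summarized by number and percentage of patients within each category". The same section asks for by-visit summary statistics at scheduled visits and a listing of abnormalities of Grade 3 or higher.

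SAP 4.8.2 names three kinds of lab table, for Part A and Part B separately: by-visit descriptive statistics, summaries by reference range indicator, and "Shift summary tables by reference range indicator". It then adds: "Unscheduled and early termination visits may not be summarized in the tables but will be presented in the listings". SAP 4.3.1 applies the same rule to non-PK outputs in general.

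SAP 3.5.1.2.1 explains the reference range flag: "The abnormal values will be flagged with 'LOW' for values below the lower limit of the local clinical reference range", with a matching HIGH flag above the upper limit. CTCAE lab toxicity appears in SAP 4.8.2 only as something that "will be graded locally according to NCI-CTCAE v5.0 or higher and included in listings". One by-subject listing is reserved for abnormalities of Grade 3 or higher.

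The introduction to protocol section 12 gives the final SAP precedence over the protocol. SAP 4.2 reports that nothing has changed.

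**The concern.** A prespecified safety table disappears without being declared. The SAP does not say that it is replacing the table. The replacement follows from leaving it out of 4.8.2 and from the precedence rule.

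Two kinds of information go with it. The first is severity: a LOW/HIGH flag puts every degree of abnormality in one direction into a single category. The second is completeness: the protocol requires unscheduled results to count towards the worst grade, while the SAP makes their inclusion in tables optional and leaves that choice open until the tables are produced. At stake is whether the lab tables in the study report show, by dose, how many patients reached each grade.

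**Working it through.** The plan states no figure for this point, so the check is a comparison of texts followed by a count of days.

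**1. The two plans side by side**

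| Feature | Protocol 12.8 | SAP 4.8.2 |
|---|---|---|
| Scale of shift | CTCAE grade | Reference range indicator |
| Post-baseline value | Maximum grade | Not stated |
| Unscheduled results in shift table | Required | May be omitted |
| By-visit statistics | Scheduled visits | By study visit; unscheduled may be omitted |
| Grade 3 or higher | Listing | Listing |

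The last two rows agree. The deviation lies in the shift table alone.

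**2. What a LOW/HIGH shift can show.** A normal-to-HIGH shift looks the same whether the post-baseline value is Grade 1 or Grade 3. If a value is already HIGH at baseline and rises further, the table shows no shift. That can happen here: exclusion criterion 16d removes only patients with ALT, AST or ALP above 1.5 × ULN, so a patient can enter with a value between 1 and 1.5 × ULN.

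**3. When labs are scheduled** (safety lab rows of protocol Tables 1 and 2, repeated in SAP Tables 8 and 9)

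- Part A: screening, D1 pre-dose, D4, D8 and early termination. None at D21.
- Part B: screening, D1, D4 and D7 (all pre-dose), D15 and early termination. None at D21 or D28.

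Days after the last scheduled lab, as a share of the days after first dose:

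- Part A: (21 − 8) / (21 − 1) = 13/20 = 65%.
- Part B: (28 − 15) / (28 − 1) = 13/27 = 48%. This span, D16 onward, contains the last two gluten-challenge days, D16 and D17.

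In these spans any lab value must come from an unscheduled or early-termination draw. If such draws are left out, no value from these days can enter a lab table.

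**4. Direction of the effect.** The maximum over some of a patient's results cannot exceed the maximum over all of them. Leaving results out of a worst-value count therefore either lowers it or leaves it unchanged. Baseline is treated differently: SAP 4.3.1 lets unscheduled pre-treatment values serve as baseline.

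**5. Size for one patient.** If one patient's only abnormality is on an omitted draw, the reported count falls from 1 to 0. As a share of the group this is:

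- 1/3 = 33.3% in a three-patient Part A cohort
- 1/6 = 16.7% among six active patients
- 1/18 = 5.6% of all active Part B patients

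The documents give no rate at which this would happen.

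**The case against.** The strongest reply is that little safety information is lost. Protocol 6.1.8 and SAP 3.5.1.2.1 require clinically significant lab abnormalities to be reported as AEs. SAP 4.8.1 then tabulates TEAEs by worst severity, counts those of Grade 3 or higher and lists all DLTs, with no restriction to scheduled visits. All lab values, their grades and a separate Grade 3 or higher listing are kept by subject. With three to six active patients per cohort, a reader can go through those listings patient by patient. The SAP wording on unscheduled visits is also permissive, and the table shells, which might settle the matter, are not available.

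Most of this stands, and it limits the point to the lab summary tables. It does not remove it. Protocol 11.2.4 says that abnormal results without clinical significance should in general not become AEs, so the AE route depends on the investigator's judgement. The grade-shift table does not. Listings also do not give numbers and percentages by grade and dose, as the protocol promised.

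A reader might infer more than the documents support:

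- **That the primary endpoint or the DLT assessment is biased.** Both are defined on AEs, not on lab shift tables.
- **That unscheduled draws hold the most abnormal values.** Some are made on clinical indication, but protocol 6.1.8 also calls for repeats to verify a finding and to follow it to resolution. Those may be less extreme than a scheduled value already tabulated.
- **That the whole gluten challenge lacks scheduled labs.** D15 is a challenge day with a scheduled safety lab, and that entry lacks the pre-challenge footnote that the D15 ECG and PK entries carry.
- **That the late gap in labs is a fault of SAP 4.8.2.** It comes from the visit schedule, and restoring the table adds no samples.

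**Conclusion.** The mismatch is real and undeclared. Under the SAP as written, the lab shift tables cannot show severity, and they can miss a worst value found only on an unscheduled or early-termination draw. The main loss is graded abnormalities that the investigator did not judge clinically significant. Nothing is lost from the listings, and clinically significant events should still reach the AE outputs.

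The conclusion that severity is missing rests only on the text. The conclusion about missed values assumes that the option to omit unscheduled and early-termination results is used. The fractions of 1/3 and 1/6 further assume a patient whose sole abnormality lies on such a draw, so they show how much one patient weighs and do not estimate an expected understatement. The study is descriptive, with no formal hypothesis test, so no inference is affected. What changes is what the lab tables report.

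**What to change.** In SAP 4.8.2, restore a table of shifts from baseline to worst post-baseline CTCAE grade, by dose, with number and percentage of patients. State that scheduled, unscheduled and early-termination results all count towards the worst grade. Keep the reference-range shifts for tests that have no CTCAE grade, and keep the by-visit statistics on scheduled visits, as the protocol has them. Add to the general rule in SAP 4.3.1 that this table is an exception.

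Correct SAP 4.2 so that it describes the lab analysis accurately. If the sponsor did intend to drop the grade shift, 4.2 should declare and justify that.

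The cost is one more table per graded lab panel. Grades are already assigned for the listings, so no new data are needed.

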3.5.1.2.1 Clinical Laboratory Evaluation

All statistical analyses of laboratory values will be performed using International System units. The Clinical laboratory parameters and tests to be analyzed locally or centrally by a certified laboratory with corresponding laboratory normal ranges are:

- Serum Chemistry: Blood urea nitrogen, creatinine, glucose, aspartate aminotransferase (AST), alanine aminotransferase (ALT), alkaline phosphatase (ALP), bilirubin (total and direct), electrolytes (sodium, chloride, bicarbonate, potassium), amylase, lipase, albumin, magnesium, calcium, and phosphorus
- Hematology: White blood cell (WBC) count, hemoglobin, hematocrit, Platelet (PLT) count, and WBC differential
- Coagulation: Prothrombin time, partial thromboplastin time or activated partial thromboplastin time, and international normalized ratio
- Complete urinalysis with qualitative analysis for protein (dipstick)
- Virus Serology: Human immunodeficiency virus (HIV), hepatitis B (HBV) (HBsAg, anti-HBc and anti-HBs), and hepatitis C (HCV) testing (Screening only)
- Serum pregnancy test will be performed at screening for women of child-bearing potential (WCBP). Serum or urine pregnancy testing for all WCBP will be performed prior to each dose.

The following laboratory tests will be performed centrally at Screening only:

- HLA DQ2.5 and HLA DQ8 testing
- Transglutaminase (tTG) and deaminated gluten peptides (DGP) IgA/IgG

For tTG, a result of <2xULN will be considered negative or weak positive. For DGP, a result of <30 U/mL will be considered negative or weak positive.

For re-screening, the HLA does not need to be repeated and the tTG and DGP antibody tests should only be repeated if >3months have elapsed from end assessment.

Unscheduled assessments should be performed as clinically indicated. For any out-of-range laboratory findings during screening, repeat laboratory testing may be performed at the discretion of the Investigator. Abnormal laboratory findings at screening should be recorded as medical history only if considered clinically significant (CS).

Investigators will assess whether the values outside the clinical reference range are clinically significant and these will be reported as abnormal NCS or abnormal CS.

- Clinically significant abnormal laboratory values will be recorded by the Investigator as AEs.

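### SAP 4.8.2 leaves laboratory change from baseline blank when a subject's unit differs from baseline and gives no conversion step, although both documents require SI units

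*SAP*

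**What the plan says.** Two places set the unit for laboratory analysis. SAP 3.5.1.2.1 says "All statistical analyses of laboratory values will be performed using International System units", and Protocol 12.8 carries the same sentence. Protocol 12.8 also makes change from baseline a required output: "Summary statistics for laboratory values including change from baseline will be tabulated for scheduled visits". SAP 4.8.2 takes this up as "Continuous descriptive statistics of observed values and change from baseline by study visit".

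At its end, SAP 4.8.2 deals with units differently. It says "There are tests with multiple standard units", adds that the unit for each test and subject is considered when baseline is derived, and then sets the rule: "Post-baseline records will not have a 'Change' value if the unit doesn't match with baseline record unit for that subject and test". Neither document describes a conversion.

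Three other places bear on the point:
- SAP 3.5.1.2.1 describes the safety tests as "to be analyzed locally or centrally by a certified laboratory with corresponding laboratory normal ranges".
- SAP 4.4.1 pools all centers, about 5 to 12 US sites.
- SAP 4.2 declares no departures from the protocol.

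**The concern.** If every analysis is in SI units, a convertible result has one analysis unit per test, and a unit mismatch with baseline should not arise. The SAP instead reports that more than one unit is present and responds by leaving the change blank. For a convertible result this discards a usable value: the measurement exists, the baseline exists, and a fixed factor links them.

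The rule also guards only part of the problem. It compares a record with the baseline of the same subject and test. It makes no comparison between subjects, and those are what a by-visit mean and SD combine.

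At stake is a protocol-required safety summary in a first-in-human trial with small dose groups, where one missing value is a visible share of the group. Laboratory change is not the primary endpoint, which is treatment-emergent adverse events (SAP 3.4.1), and no escalation rule uses it.

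**Working it through.** The plan gives no figure on this point, so there is none to reproduce. The check is a comparison of text, followed by simple shares.

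**1. Do the statements conflict?** SAP 3.5.1.2.1 and Protocol 12.8 require SI units for all laboratory analyses. SAP 4.8.2 accepts several units per test and gives a rule that operates only when they differ within a subject. Protocol 12 lets the final SAP prevail over the protocol, but that does not settle the matter, because both statements stand in the SAP.

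**2. Share of change values lost, for one test at one visit.** Group sizes are from SAP 3.2. With k mismatched patients among n, share lost = k/n. For k = 1:

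| Group | n | Share lost |
|---|---|---|
| Part A cohort, not expanded | 3 | 1/3 = 33.3% |
| Part A cohort, expanded, or Part B active cohort | 6 | 1/6 = 16.7% |
| Part B pooled placebo (3 cohorts × 2) | 6 | 1/6 = 16.7% |
| Part B pooled KAN-101 (3 cohorts × 6) | 18 | 1/18 = 5.6% |

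After conversion to a common unit, the loss through unit mismatch is 0 of n for convertible tests.

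**3. Share of the whole panel.** The rule works by record, so one mismatch does not remove a patient's other tests. SAP 3.5.1.2.1 and 4.8.2 give at least 18 chemistry, 4 hematology (before the differential), 3 coagulation and 2 urinalysis parameters: 18 + 4 + 3 + 2 = 27. One mismatched test in one patient is then at most 1/(3 × 27) = 1/81 = 1.2% of a 3-patient cohort's change values at that visit, and 1/(6 × 27) = 1/162 = 0.6% with six patients.

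**4. What the rule lets through.** Take two subjects at different sites. Each is reported in one unit throughout, but the two units differ. Each matches "match with baseline record unit for that subject and test" in the sense of the rule, so both keep their change values. Their observed values and changes then enter the same by-visit mean, and SAP 4.8.2 states no split by unit.

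**5. How large could that effect be?** The documents name neither tests nor units, so this is an illustration on assumed data. Take six SI values 4.4, 4.7, 4.9, 5.1, 5.3 and 5.6, with mean 30.0/6 = 5.0 and SD 0.43. Leave the last in another unit with assumed factor f. The mean is then (24.4 + 5.6f)/6.

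| Assumed f | Mean | Ratio to 5.0 | SD |
|---|---|---|---|
| 2 | 35.6/6 = 5.9 | 1.2 | 2.6 |
| 10 | 80.4/6 = 13.4 | 2.7 | 20.9 |
| 18 | 125.2/6 = 20.9 | 4.2 | 39.2 |

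These figures show sensitivity only. They say nothing about how often units differ.

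**The case against.** The strongest reply is that the SAP speaks of standard units, not reported units. On that reading SI conversion has already been done, and the rule is a residual guard against subtracting results that are not comparable. The panel includes a white-cell differential, which can be given as a percentage or as an absolute count, and no fixed factor joins those two. This reading is possible, but the SAP neither states it nor defines the term. Even if it is meant, a percentage and a count should be separate parameters, each with its own baseline and change. Leaving the change blank would still lose a change value wherever the subject has a pre-treatment result in the same form.

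Several other parts of the reply stand:

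- A reader might infer that safety laboratory data are lost outright. The documents do not support that. Only the derived change is blank. Observed values, reference-range summaries, shift tables, locally assigned grades and full listings remain, and clinically significant abnormal values are recorded as adverse events.
- A reader might take 1/3 or 1/6 as the share of all change data in a cohort. Those shares hold only for one test at one visit; step 3 of the working gives the panel share.
- A reader might conclude that the observed-value summaries will mix units. The SAP does not say so. The inference comes from a missing rule, the SI sentence covers those summaries too, and the table shells may split by unit.
- Local or central testing makes differing units plausible, but the documents do not say that any patient's laboratory or unit changes during the study.

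**Conclusion.** The point holds within these limits. SAP 4.8.2 contains a rule that is inconsistent with the SI requirement in SAP 3.5.1.2.1 and Protocol 12.8, and no conversion step reconciles them. Where the results are convertible, the rule discards change values needlessly.

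Its size depends on a count that the documents do not give. It ranges from no affected record up to every patient whose reporting unit for a test changed after baseline. Mixing of units between subjects is a possibility that the SAP leaves open, not a planned or demonstrated error.

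This should be corrected because the remedy is cheap and the groups are small. It does not threaten the primary endpoint, the dose-escalation decisions or the by-subject record of laboratory safety.

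**What to change.** Replace the unit rule in SAP 4.8.2 with text such as:

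> All numeric results are converted to one SI unit per parameter before deriving baseline, change and by-visit summaries. Results that cannot be converted (e.g. percent versus absolute count) are defined as separate parameters, each with its own baseline. Change is missing only where no conversion exists. Original values and units are kept in the listings.

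Local CTCAE grading and local reference-range flags stay as planned, since neither needs a common unit across subjects or visits. The cost is the SAP wording and a conversion table for the laboratory dataset. No new data are needed.

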4.8.3 Physical Examination, Vital Signs and ECG

For Part A (SAD) and Part B (MAD) separately, categorical and continuous descriptive statistics of observed values and change from baseline will be presented for:

- Each vital sign measurement by scheduled study visit and change from baseline.
- Each physical examination measurement by scheduled study visit (Normal, Abnormal, Not done).
- Each ECG measurement by scheduled study visit (Normal, Abnormal Non-Clinically Significant (ANCS), Abnormal Clinically Significant (ACS))

The following by-subject listings will be provided by study part and treatment group on enrolled subjects:

- Vital Signs (values and change from baseline)
- Physical Examination (screening and as clinically indicated)
- ECG

4.8.4 Prior and Concomitant Medications and Procedures

All prior and concomitant medications including dose, form, route of administration, frequency and indication will be provided in a by-subject listing for each study part and treatment group for prior and concomitant medications by ATC Levels and PT on enrolled subjects.

For Part A (SAD) and Part B (MAD) separately, summary tables will be provided by treatment group for prior and concomitant medications by ATC Levels and PT on ATAS.

